### **Research hypotheses**

 $H_01$ : There is no difference in lung functions between the intervention group of elderly individuals subjected to breathing exercises, and those in the control group.

 $H_02$ : There is no difference in cardiac functions between the intervention group of elderly individuals subjected to breathing exercises, and those in the control group.

 $H_03$ : There is no difference in sleep quality between the intervention group of elderly individuals subjected to breathing exercises, and those in the control group.

 $H_04$ : There is no difference in subjective vitality between the intervention group of elderly individuals subjected to breathing exercises, and those in the control group.

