Official Title of the study: Effect of breathing exercise on some physiological parameters, sleep quality and vitality in elderly.

NCT number: not yet have

Date of the document: January 1, 2019

Study population and sample

The population of the study consists of 294 individuals living in the 75th Year Nursing Home Elderly Care and Rehabilitation Center affiliated to Ankara Provincial Directorate of Family and Social Policies. In the sample calculation of the study, taking into account the results of similar studies in the literature with the GPower 3.1.9.4 program, it was calculated that it would be sufficient to take a total of 52 individuals, with a margin of error of 0.05, 80% test power, 26 elderly individuals per group. Considering that such studies may be lost in the process, 20% of the minimum sample number (11 individuals) was added to the study in order not to decrease the statistical power of the research. A total of 32 elderly individuals in the intervention group and 31 elderly individuals in the control group were planned.

Stratified randomization method will be used in the research. Elderly individuals who meet the inclusion criteria will be separated into layers by considering the age (65-74 years -75 years and older) and gender (women-men) after the pre-test data are obtained, and then by simple randomization method using SPSS program in computer environment. will be assigned to the intervention and control groups.

Data collection tools

Research data will be obtained by using the data collection tools mentioned below.

- Introductory Information Form
- Pittsburg Sleep Quality Index (PSQI)
- Subjective Vitality Scale (SVS)
- Physiological Parameters Evaluation Form

Introductory information form

The form was created by the researcher by examining the related literature. In this form, there are 9 closed-ended questions that question the socio-demographic characteristics, health conditions and habits of the elderly.

Pittsburg sleep quality index (PSQI)

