Pittsburg Sleep Quality Index (PSQI) was developed by Buyse et al. In 1989 and its adaptation to Turkish, validity and reliability study was done by A arg n et al. The scale that determines the quality of sleep consists of 18 self-report questions and evaluates the quality of sleep in the last 4 weeks. PSQI has 7 components such as subjective sleep quality, sleep latency, sleep duration, habitual sleep effectiveness, sleep disturbance, use of sleep medication, daytime dysfunction and each component is evaluated between 0 and 3 points. The total score ranges from 0-21. The total score higher than 5 indicates that the sleep quality is bad. The sensitivity of the scale was 89.6%, and its selectivity was 86.5%. Cronbach internal consistency coefficient of the scale is 0.80 in the Turkish validity and reliability study and later studies.

Subjective vitality scale (SVS)

Subjective Vitality Scale (SVS) The scale was developed by Ryan and Frederick in 1997, and its validity and reliability study was performed by Uysal et al. (2014). Z is a 7-point Likert (1 absolutely disagree-7 strongly agree) measurement tool based on self-report, consisting of 7 items. By collecting the points of all items in the scale, the total subjective fitness score of the individual can be obtained. The second item of the scale is reversed. The scale in the scale ranges from 7 to 49. High scores obtained from the scale indicate that the individual's subjective fitness level is high. Cronbach internal consistency coefficient of the scale is 0.87. The test-retest correlation coefficient was found to be 0.79. In the explanatory factor analysis applied for the construct validity of the scale, it was determined that the items were collected in one factor and the single factor model explained 62% of the total variance. Confirmation factor analysis result fit index values 2 = 19.95, sd = 8; RMSEA = 0.08, AGFI = 0.93, GFI = 0.97, NFI = 0.98.

Physiological parameters evaluation form

As physiological parameters;

• It is a form prepared by the researcher to evaluate lung functions. In this form; forced vital capacity (FVC), air volume removed in the 1st.second of forced expiration (FEV1), FEV1 / FVC ratio and percentages

• In the form created to evaluate cardiological functions; heart rate, blood pressure, heart rate, oxygen saturation are forms to evaluate and record.

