Cardiac functions will be evaluated using a manual sphygmomanometer and a pulse oximeter, while pulmonary functions will be assessed by a physiotherapist using a spirometer.

Dependent variables

Respiratory function test results, systolic / diastolic pressure, heart rate and oxygen saturation, the score obtained in the Pittsburg Sleep Quality Index, and the Subjective Vitality Scale are dependent variables of the study.

Independent variable

The breathing exercise program is the independent variable of the study.

Evaluation of the data

The data will be evaluated using SPSS (Statistical Package for Social Sciences) 16.0 package program. For descriptive statistics, frequency, percentage values, average and standard deviation will be used. Chi-square test will be used for categorical comparisons. In the statistical evaluation of quantitative variables, the compatibility of the data with the normal distribution will be examined with the Kolmogorov Smirnov test. If the data are suitable for normal distribution, whether the Pittsburg Sleep Quality Index score, Subjective Fitness Scale score, pulmonary function test results, systolic / diastolic pressure, heart rate and oxygen saturation values change between the intervention and control groups before and after respiratory exercise, the significance of the difference between the two partners is important. Intra-group change will be evaluated by t-test in dependent groups and two-way analysis of variance in repeated measurements of groups. The level of significance will be taken as p < 0.05. The effect size will be determined by Cohen's d value. In general, if the d value is less than 0.2, it is defined as a weak effect, medium if 0.5, and strong if it is greater than 0.8. In the evaluation of bidirectional variance analysis, partial eta square (p 2) will be used as the effect value. Generally, if the value of p 2 is less than 0,01, the effect size is weak, it is defined as medium if it is 0,060, and strong if it is greater than 0,140.

In order to prevent bias in the evaluation of the data, the data recorded in the database will be analyzed by a statistical expert independent of the researcher. The data will be sent to the statistical specialist by coding as "Group 1" and "Group 2", without specifying the name of the intervention and control groups.

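### The SAP names no deciding between-group test for H01–H04 and leaves the pre-test value, age stratum and sex out of the analysis; one adjusted ANCOVA per outcome would mend both

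*SAP*

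**What the plan says.** The Protocol's Research hypotheses are all between-group nulls. H01, for example, begins "There is no difference in lung functions between the intervention group of elderly individuals", and H02 to H04 follow the same form for cardiac function, sleep quality and vitality.

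The SAP section Evaluation of the data takes up the comparison in one sentence, which asks whether the "values change between the intervention and control groups before and after respiratory exercise, the significance of the difference between the two partners is important". No recognisable test is attached to it. The next sentence reads: "Intra-group change will be evaluated by t-test in dependent groups and two-way analysis of variance in repeated measurements of groups". Partial eta squared is to accompany the ANOVA, and Cohen's d is the other effect measure. Nothing states which ANOVA term, or which test, decides a hypothesis.

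Under Study population and sample, the SAP stratifies the randomisation "by considering the age (65-74 years -75 years and older) and gender (women-men) after the pre-test data are obtained". The pre-test values and both strata are therefore known before allocation. None is mentioned again as a covariate.

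**The concern.** A two-group, two-occasion repeated-measures ANOVA yields three tests. The group-by-time interaction is a treatment contrast. The group effect averages pre-test and post-test, so it carries only half the treatment effect. The time effect is not a treatment contrast. Add an independent comparison of post-test values, which the unclear sentence may intend, and several candidates with very different power stand side by side. Without a stated choice, the deciding test can be picked after the p-values are known.

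The paired t-tests are not marked as descriptive, and they do not test H01–H04.

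Finally, the pre-test enters only as a repeated response. Used as a covariate, it would sharpen the between-group estimate with data the trial already collects.

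**Working it through.** **Inputs from the documents.** The SAP sets the level by "The level of significance will be taken as p < 0.05" (two-sided is assumed here, since sidedness is not stated) and the size "with a margin of error of 0.05, 80% test power, 26 elderly individuals per group", with 32 and 31 planned after the loss allowance.

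**Inputs that are missing.** The effect size is attributed only to published work ("taking into account the results of similar studies in the literature with the GPower 3.1.9.4 program"), and no pre-post correlation ρ is given. The nearest figure is for the vitality scale: "The test-retest correlation coefficient was found to be 0.79". That is not a 12-week pre-post correlation. Both quantities are therefore varied.

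**The plan's own figure.** The 26 per group cannot be reproduced from stated inputs. Several settings fit it: a two-sided two-sample t-test at 0.8 SD (power 80.7%), a one-sided one at 0.7 SD, and a repeated-measures interaction with f = 0.2 and correlation 0.5 (total 52). The sample size therefore does not reveal which test was intended.

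**Formulas.** Take equal SD at both occasions and a true post-test difference of δ SD. The standardised effects are:

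- post-test only: δ
- interaction (identical to a t-test on change): δ/√(2(1−ρ))
- ANOVA group effect: (δ/2)/√((1+ρ)/2)
- ANCOVA: δ/√(1−ρ²), with 52 − 5 = 47 df instead of 50

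ANCOVA is never the larger in variance, apart from the small-sample cost: 2(1−ρ) − (1−ρ²) = (1−ρ)² ≥ 0, and 1 − (1−ρ²) = ρ² ≥ 0. Its variance relative to the interaction is (1+ρ)/2. The interaction beats post-test only when 2(1−ρ) < 1, that is, when ρ > 0.5.

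**Example at δ = 0.8, ρ = 0.5, 26 per arm.** The noncentrality is the effect times √(26·26/52) = √13 = 3.606.

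- Interaction: 0.8/√1 = 0.80, noncentrality 2.88, power 81%
- ANCOVA: 0.8/√0.75 = 0.924, noncentrality 3.33, power 90%
- Group effect: 0.4/√0.75 = 0.462, noncentrality 1.67, power 37%

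**Power, 26 per arm, 0.8 SD**

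| ρ | Post-test only | Interaction | ANCOVA | Group effect | Variance ratio ANCOVA/interaction |
|---|---|---|---|---|---|
| 0.3 | 81% | 67% | 84% | 42% | 0.65 |
| 0.5 | 81% | 81% | 90% | 37% | 0.75 |
| 0.7 | 81% | 95% | 98% | 34% | 0.85 |
| 0.79 | 81% | 99.2% | 99.6% | 32% | 0.895 |

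**Other settings, interaction vs ANCOVA, same order of ρ**

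- 32/31 and 0.8 SD: 75 vs 91%, 88 vs 95%, 98 vs 99%, 99.8 vs 99.9% (post-test only 88%)
- 26 per arm and 0.5 SD: 32 vs 46%, 42 vs 53%, 63 vs 70%, 78 vs 82% (post-test only 42%)
- Smallest difference with 80% power, 26 per arm: 0.94 vs 0.76, 0.79 vs 0.69, 0.61 vs 0.57, 0.51 vs 0.49 SD (post-test only 0.79)

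**Simulation check.** The formulas ignore chance imbalance in the covariates. Simulated trials with 26 per arm and two strata that predict nothing give ANCOVA power of 82, 89, 97 and 99.4% at 0.8 SD, and about 43, 50, 67 and 79% at 0.5 SD. Type I error stays close to 5%.

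**Cost of the open choice.** In simulated null trials each test alone rejects in about 5%. Declaring success if either the post-test or the interaction test is significant rejects in about 9%; adding the group effect gives about 11%.

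**Paired tests, only if read as evidence.** If each arm's paired test is significant with probability q under the null, the pattern of intervention significant and control not has probability q(1−q). With no time shift this is 0.05 × 0.95 = 4.75%. With an assumed shift of 0.2 to 0.5 SD common to both arms (ρ 0.5 to 0.7), it is 10 to 25%.

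**The case against.** The strongest reply is that the plan already holds a usable test. Asking whether values change differently between groups from before to after, and naming a two-way repeated-measures ANOVA, points to the interaction. One sentence saying so would close the gap without ANCOVA. The unclear phrase may be a translation of an independent-samples t-test. The paired tests are labelled intra-group and are nowhere tied to H01–H04, and nobody proposes to read the group effect as the treatment test.

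Much of this is fair. The group-effect and paired-test figures rest on readings the SAP does not clearly propose, and they carry little weight here. But if the phrase does mean an independent t-test, two between-group tests remain unranked, which is the concern itself. Sending the analyst neutrally coded groups hides direction; it does not hide which test reaches significance.

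On ANCOVA, it is true that the gain depends on an unknown ρ and is slight against the interaction near 0.8. It is also true that nearly all of it comes from the pre-test value. Strata that predict nothing cost roughly 1 to 2.5 power points, and at 0.5 SD and ρ = 0.3 the simulated gain over post-test only is about one point. At ρ of 0 to 0.1 the stratum-adjusted ANCOVA falls slightly below post-test only (78–79% against 81% at 0.8 SD). Even so, each existing candidate loses clearly somewhere: the interaction at low ρ, post-test only at high ρ. ANCOVA avoids having to guess.

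The Protocol's Pre-test section mentions both groups, which sits awkwardly with randomisation afterwards. The pre-test nevertheless precedes the exercise (29.01–03.02.2019 against 18.02.2019), so it is still a proper baseline.

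**Conclusion.** The concern holds, as a loss of clarity and efficiency rather than an invalid analysis. The SAP names no deciding test for its between-group hypotheses and uses none of the three covariates it has before allocation. Leaving post-test and interaction both open allows about 9% false positives if the smaller p-value is taken.

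At 26 per arm and 0.8 SD, ANCOVA adds 17 points of power over the interaction at ρ = 0.3 (84 − 67) and 0.4 at ρ = 0.79 (99.6 − 99.2). Over post-test only it adds 3 points (84 − 81) and about 19 (99.6 − 81). These sizes rest on an assumed effect and correlation, equal variances and two-sided 5% tests. The contribution of the strata cannot be computed from the documents; it may be small for the spirometry percentages, which the device already references to age, height and gender.

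**What to change.** In Evaluation of the data, for each continuous dependent variable:

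- Name one deciding test: the arm coefficient, as an adjusted mean difference with 95% CI, from a linear model of the post-test value on arm, own pre-test value, age stratum (65–74, 75 and older) and sex.
- State that this coefficient replaces the ANOVA group, time and interaction tests for judging H01–H04.
- If the repeated-measures ANOVA is kept, say that only its group-by-time interaction is read, as a secondary analysis.
- Report within-group changes descriptively, and Cohen's d for the between-group difference.

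The cost is SAP wording and three degrees of freedom, plus a possible 1 to 2.5 points of power if the strata prove unrelated to outcome. No visit or measurement is added.

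Two matters remain for separate decisions: which variable decides H01 and H02, each of which covers several measures, and what is done if the normality condition attached to the planned tests fails.

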### Post-test

One day after the end of breathing exercise application, between the dates 10.05.2019 - 14.05.2019, elderly individuals will be called by calling from the room telephones in the physical therapy unit. will be re-evaluated in individuals in both groups

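### With no rule for missing post-tests, the planned paired t-test and repeated-measures ANOVA compare the arms on completers, and the allowance of 11 people protects power but not comparability

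*SAP*

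**What the plan says.** The SAP's sample-size paragraph (Study population and sample) sets a minimum of 52 people and gives the basis as "with a margin of error of 0.05, 80% test power, 26 elderly individuals per group". Because people may be lost, "20% of the minimum sample number (11 individuals) was added to the study in order not to decrease the statistical power of the research". The planned arms are 32 (intervention) and 31 (control). Assignment follows the pre-test, so everyone randomised has a pre-test value.

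The SAP's Evaluation of the data section gives the outcome methods: "Intra-group change will be evaluated by t-test in dependent groups", together with the "two-way analysis of variance in repeated measurements of groups". The significance threshold is 0.05, and the software is SPSS 16.0. One further phrase there, on the difference between two partners, is too broken to tell whether it means a paired or a two-sample test.

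The protocol has a single post-test on 10-14 May 2019, when outcomes "will be re-evaluated in individuals in both groups". Under Study design and participants it separates from the study anyone who develops a listed condition during the exercise program.

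Neither document defines an analysis population, mentions intention to treat, gives a missing-outcome method or sensitivity analysis, or says whether people who stop are post-tested.

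**The concern.** The plan treats loss only as a threat to power. Adding people replaces lost numbers, but it does not make those who remain in one arm comparable with those who remain in the other.

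The arms differ in what could cause loss. The intervention arm has 12 weeks x 3 days = 36 supervised sessions; controls have none. The separation rule is worded around the exercise program, and the text does not say whether controls are watched in the same way. Refusal, a hospital stay or absence in the five-day post-test window would also remove a person from both named analyses.

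If the exercisers who leave are those doing worst, the completers can show a gain in lung function, sleep or vitality that reflects who stayed. If they are those who started worst, a real gain can be hidden. Under the SAP as written, neither case would be visible in the result.

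**Working it through.** **1. The plan's own figures.** 0.20 x 52 = 10.4, rounded up to 11; 52 + 11 = 63 = 32 + 31. The allowance is 11/63 = 17.5% of those randomised. No effect size is given, so the 52 cannot be checked directly. If it came from a two-sided two-sample t-test (assumption), 26 v 26 at 80% power implies d = 0.79. At that d, 32 v 31 has 87% power. For power, then, the allowance does what the SAP says.

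**2. Who enters the analysis.** A paired t-test needs both values by definition, and classical repeated-measures ANOVA in SPSS drops incomplete cases. Since everyone has a pre-test, the set analysed is everyone with a post-test. A two-sample test at post-test, if the broken phrase means that, would use the same set.

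**3. Hand calculation.** If k of n people in one arm are lost, and their mean change differs by g SD of change from those who stay, the completer mean moves by (k/n) x g. With 6 of 32 exercisers lost selectively and 5 of 31 controls lost at random:
- g = 0.5: 6/32 x 0.5 = 0.09 SD; false positives 6%. If the shift masks a true d of 0.79, power falls from 80% to 70%.
- g = 1.0: 6/32 x 1.0 = 0.19 SD; false positives 10%, or power 57%.

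**4. Simulation.** Assumptions, none taken from the documents:
- 32 v 31, no true effect, bivariate normal pre- and post-test, correlation r = 0.5-0.7, 4,000 runs per scenario;
- controls lost at random;
- exercisers' log-odds of loss rise by 1-1.5 per SD of the driver;
- 6 v 5 or 8 v 3 lost;
- higher scores are better (reverse the sign for the sleep index).

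Bias is in SD of a single measurement.

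| Exercisers more likely to be lost | Bias of completer change | False positives |
|---|---|---|
| Worst change | about +0.12 to +0.30 | 9-21% |
| Worst pre-test | about -0.05 to -0.16 | 6-8% |
| Worst post-test | about +0.06 to +0.15 | 6-9% |
| Unrelated to outcome | 0 | about 5% |

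**5. What pre-test adjustment would do.** Let s be the shift that selection causes in the exercisers' mean on the driver.
- Loss driven by the pre-test: the post-test mean shifts by rs. Bias of change = rs - s = -s(1-r); adjusted bias = rs - rs = 0.
- Loss driven by the post-test: the pre-test mean shifts by rs. Bias of change = s(1-r); adjusted bias = s - r(rs) = s(1-r^2). The adjusted bias is larger by the factor 1+r, that is 1.5 to 1.7. In simulation it is 0.09-0.23 SD, against 0.06-0.15 SD for change.
- Loss driven by change: adjusted bias is (1+r)/2 of the change bias, that is 0.75 to 0.85 of it, so most remains.

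Adjustment also improves precision. For a true effect of 0.5 SD, power rises from 43% to 53% at r = 0.5 and from 64% to 69% at r = 0.7.

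**The case against.** The strongest reply has four parts.

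*Loss may be small.* All participants live in one home, are called to the post-test by room telephone, and can make up missed sessions. This stands in part. Bias scales with actual loss, and the 11 is a rounded 20% allowance with no split by arm. A reader might infer that the SAP forecasts 11 losses, or heavier loss among exercisers; it says neither. Make-up sessions, however, deal with missed exercise, not missing outcomes, and the SAP itself thought loss likely enough to recruit for it.

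*The sizes are assumed.* This stands. No passage supports a selection strength or an 8 v 3 split. With weaker selection on change (log-odds 0.5 per SD, 6 v 5 lost), the bias is 0.08-0.10 SD with 7-8% false positives.

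*A mixed model is not the cure.* This stands. With one post-test, a person with only a pre-test adds almost nothing to the contrast, and step 5 of the working shows that adjustment can increase bias when loss follows the unseen post-test. Obtaining the post-tests matters more than the model.

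*The statistician sees the arms only as Group 1 and Group 2.* This does not answer the point: coding masks the analyst but does not supply missing outcomes.

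**Conclusion.** The point holds as a gap in the plan. The named methods, with no analysis set and no missing-outcome rule, yield a completer comparison, and the added 11 people do not restore comparability. The SAP does not itself announce a completer analysis; this follows from its methods and its silence.

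A reader might go further and conclude that the trial will report a false benefit. The documents do not support that. They give no loss rates by arm and no reasons for loss; if loss is unrelated to outcome there is no bias, and if it follows a poor pre-test the bias runs against exercise. Under the stated assumptions the range is about -0.16 to +0.30 SD, with 6-21% false positives. For scale, the target implied by 26 per group is about 0.79 SD, itself an assumption and in the units of whatever comparison was powered. The gap is certain and its size is not, so this is a change the sponsor should make rather than a fatal flaw.

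**What to change.** 1. **Protocol, Post-test:** state that the post-test is sought from everyone randomised, including those who stopped exercising, where they remain willing and able. This concerns outcome collection only; it leaves the rule for stopping exercise, and any clinical judgement of fitness for a measurement, as they are.
2. **SAP, Evaluation of the data:** analyse everyone in the arm assigned, whatever number of sessions they attended.
3. **Same section:** make the between-arm test a pre-test-adjusted comparison (ANCOVA, or a mixed model with a common pre-test mean). State that it gains precision and removes bias from loss explained by the pre-test, but does not protect against loss that depends on the unseen post-test, where it can be more biased than the change comparison.
4. **Same section:** add a sensitivity analysis for missing post-tests in both arms. Give lost exercisers the control-arm mean change, then progressively worse values, and vary lost controls too. Report where the conclusion changes, and report losses by arm with reasons.

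Cost: a few sentences, a few hours of analysis with standard software, and some effort to reach residents who stopped. No new participants or staff are needed. The downside is that the sensitivity result may be less favourable than the completer result.

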• Blue, black, green, brown, red nail polish, if any, in the individual before the oxygen saturation measurement is deleted, artificial nail is removed,

- It is placed on the hand and / or toenail of the light source part of the pulse oximeter,
- Measurements are made for 30 seconds and then the device is removed from the finger
- The data are recorded on the data form created by the researcher.

Evaluation of lung functions will be done in the presence of a specialist physiotherapist. The specialist physiotherapist does not know the elderly individuals in the experimental and control groups. Spirometry will be used to evaluate lung function. Spirometry is the basic device of respiratory function test laboratories. It consists of the electronic part where the measurement is made and the mouthpiece that the patient breathe. Cosmed Pony FX - Desktop Spirometer and disposable mouthpieces suitable for the device will be used in the study. This type of spirometer enables testing without the need for a computer. It has an internal memory where patient information can be stored. It is used with two-way digital turbine flowmeter. Pulse function test measurement application steps are as follows;

- Elderly individuals are informed before spirometry is applied.
- The height of the elderly person, body weight is measured and recorded with his age
- Individual disposable mouthpiece is placed in the entry section of the tool.

• The individual puts the mouthpiece in his mouth with his lips, but not to bite with his teeth. It is important that the lips close well. Otherwise, leakage will occur. This causes incorrect measurement.

• The nose of the individual who is connected to the spirometer device with the help of a mouthpiece is closed with a special latch before the measurement.

- The individual breathes calmly first (4-5 times)
- It takes a hard, deep and fast breath after normal breathing.

• It is also fast, challenging and exhaled with the command to exhale. Breathing should take at least 6 seconds.

• This process must be repeated at least 3 times.

The test results are compared with the expected values (predicted values) pre-calculated in healthy individuals of the same age, height and gender by the software found in the spirometer

device and expressed as a percentage of these values. The obtained results will be sent to the researcher within 15 days in pdf format by the authorized firm of the spirometer device.

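### The lung and cardiac hypotheses (H01, H02) are each one null tested on several unranked variables, and no rule says what rejects them

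*SAP*

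**What the plan says.** The Protocol, under Research hypotheses, sets out four nulls. The first begins "There is no difference in lung functions between the intervention group" and the second "There is no difference in cardiac functions between the intervention group". Neither names a variable.

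The SAP, under Physiological parameters evaluation form, lists the lung measurements as "forced vital capacity (FVC), air volume removed in the 1st.second of forced expiration (FEV1), FEV1 / FVC ratio and percentages". The cardiac form covers "heart rate, blood pressure, heart rate, oxygen saturation are forms to evaluate and record"; heart rate is printed twice and counts once. The list of dependent variables separates systolic from diastolic pressure and ranks nothing.

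Under Evaluation of the data, the SAP asks whether "pulmonary function test results, systolic / diastolic pressure, heart rate and oxygen saturation values change between the intervention and control groups". It mentions paired t-tests for within-group change and a two-way repeated-measures analysis of variance, and then gives a single criterion: "The level of significance will be taken as p < 0.05".

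The SAP's sample-size paragraph ties the 26 per group to no endpoint, so a deciding variable cannot be inferred from there. The text available for review contains no primary endpoint, composite, global test, multiplicity adjustment, or any/all rule.

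**The concern.** A hypothesis needs a rule that turns results into a decision. H03 and H04 each rest on one total score (PSQI, SVS), so only the choice of test is open there. H01 and H02 rest on several variables each, and the plan does not say which of them, or how many, must reach p < 0.05.

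Suppose FEV1 gives p = 0.03 while FVC and the ratio do not. The plan allows H01 to be reported as rejected (one variable differs), as not rejected (most do not), or as undecided. The choice can be made after the results are known. It also fixes the error rate: an any-one rule gives several chances of a false positive, and an all-variables rule gives very few. Two of the four declared hypotheses therefore have no defined answer and no defined type I error.

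**Working it through.** **Inputs from the documents.** Lung: k = 3 (FVC, FEV1, FEV1/FVC). Cardiac: k = 4 (systolic, diastolic, heart rate, saturation). Level 0.05 per test. Group sizes 26/26 (the minimum) or 32/31 ("A total of 32 elderly individuals in the intervention group and 31 elderly individuals in the control group were planned"). The lung count is a minimum: the SAP adds percentages, and the Protocol says spirometry results are compared with predicted values by the "device and expressed as a percentage of these values". These are not counted below.

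**Assumptions, not in the documents.** Two-sided tests, the correlations between variables, and a standardised difference d of 0.8 for power. Only between-group tests are counted.

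**The plan's own figure.** The effect size behind 26 per group is not given, so the figure cannot be reproduced from stated inputs. A two-sided t-test at 0.05 with 80% power needs 26 per group at d = 0.8, so that value is used for illustration. The addition does reproduce: 0.20 × 52 = 10.4, taken as 11, and 52 + 11 = 63 = 32 + 31.

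**Any-one rule, no true effect, H02.** With independent variables the rate is 1 − (1 − 0.05)^k. For k = 4 this is 1 − 0.95⁴ = 18.5%. With equal correlation r, it is 1 − ∫ φ(u)·[Φ((1.96 − √r·u)/√(1−r)) − Φ((−1.96 − √r·u)/√(1−r))]^k du:

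| Assumed r | H02, k = 4 |
|---|---|
| 0.9 | 9.4% |
| 0.5 | 15.6% |
| 0 | 18.5% |

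Simulated two-sample t-tests at 26/26 and 32/31 agree to within about 0.2 percentage points.

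**Any-one rule, no true effect, H01.** Equal correlation does not suit two volumes and their own ratio. Take log(FEV1/FVC) = log FEV1 − log FVC with equal SDs and correlation ρ between the two logs. The ratio then has correlation √((1−ρ)/2) with FEV1 and the negative of that with FVC, which is ±0.32 at ρ = 0.8 and ±0.16 at ρ = 0.95. Simulated t-tests give:

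| Assumed ρ | 26/26 | 32/31 |
|---|---|---|
| 0.8 | 11.9% | 12.0% |
| 0.9 | 11.3% | 11.2% |
| 0.95 | 11.0% | 11.1% |

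The independence value, 1 − 0.95³ = 14.3%, is not a realistic figure for these three variables.

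**All-variables rule.** Rejection requires each test to be significant, so the rate cannot exceed that of any single test: at most 5%.

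**Power for one variable.** The noncentrality is d·√(n₁n₂/(n₁+n₂)). For 26/26 it is 0.8 × √13 = 2.88 (50 df). For 32/31 it is 0.8 × √(992/63) = 3.17 (61 df).

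| Level | 26/26 | 32/31 |
|---|---|---|
| 0.05 (deciding endpoint) | 80.7% | 87.8% |
| 0.05/3 = 0.0167 (lung, Bonferroni) | 65.8% | 76.0% |
| 0.05/4 = 0.0125 (cardiac, Bonferroni) | 61.7% | 72.4% |

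**The case against.** The strongest reply is that the plan promises less than this criticism supposes. The 0.05 is the threshold for each test, and no passage promises a 5% error rate for H01 or H02 as a whole. The variables are listed in advance and effect sizes are planned. The SAP can be read as variable-by-variable reporting under two topic headings, and the inflation needs an any-one rule that no passage states.

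Much of this stands. A reader might infer that the SAP breaches a stated 5% error rate for these hypotheses; the documents do not support that, because the stated level is per test. Nor do they support a demand for adjustment across all four hypotheses, since no joint error rate is claimed.

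What does not stand is that the gap is harmless. If the variables are only reported one by one, H01 and H02 are never decided, although the Protocol makes them the study's hypotheses. A null of no difference in lung functions is false as soon as one lung function differs, so the any-one reading is the natural one.

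Sending data coded as two unnamed groups to an independent statistician limits bias in the analysis but supplies no rule. It masks only the statistician. The researcher teaches the exercises, so knows the allocation, and also receives the spirometry reports before any transfer.

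**Conclusion.** The point holds in this form: the decision rule for H01 and H02 is undefined, and its most natural completion inflates the false-rejection rate. Under the any-one rule the rate is about 11-12% for H01 (ratio modelled from FEV1 and FVC, assumed correlation 0.8 to 0.95) and 9.4-18.5% for H02 (assumed equal correlation 0.9 down to 0). Under an all-variables rule it is at most 5%. The correlations are assumptions, and the absence of a rule is judged on the supplied text.

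This should be corrected, because it determines whether two of the four hypotheses have a defined answer. It does not affect the validity of the data. H03 and H04 have no multiple-endpoint problem, but the same unclear wording on tests governs them.

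**What to change.** Before any post-test measurement is taken (Protocol, Post-test), name in the SAP one deciding endpoint for H01 and one for H02, each judged by one named between-group test at two-sided 0.05. Report the other lung and cardiac variables, the percent-predicted versions and the within-group tests as exploratory. State the same named between-group test for PSQI (H03) and SVS (H04). Fixing the rule only before transfer to the statistician would be too late, because the researcher can by then have seen results by group.

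If the sponsor prefers to let any listed variable count, apply Holm or Bonferroni within each hypothesis instead. The two agree on whether the hypothesis itself is rejected, since Holm's first step is the Bonferroni test.

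Either route changes wording only, with no change to sample or measurements. At an assumed d of 0.8:

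- **Deciding endpoint:** it keeps 81% power (26/26) or 88% (32/31). The price is that an effect confined to another variable can no longer reject the hypothesis. In that case the chance of rejecting is 5%, against 83-85% (26/26) or 89-91% (32/31) under an unadjusted any-one rule.
- **Bonferroni:** per-variable power is 66% (lung) and 62% (cardiac) at 26/26, or 76% and 72% at 32/31, whichever variable carries the effect.
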